3.4 STATISTICS & RANDOMIZATION

Using log rank statistics with a power of 80 % and a type I error of 5%, 1275 patients are needed to detect a difference between both treatment arms of 5% in locoregional recurrence rate 3 years postoperatively, assuming a 10% recurrence rate in the open group. Randomization will be 2:1, laparoscopic versus open resection respectively. Analyses will be on "intention to treat" basis. Randomization is stratified for each participating center, planned procedure, radiotherapy and sex.

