4.5 ADJUVANT THERAPY

Extensive studies have been performed throughout the years to investigate the efficiency of many different regimes in controlling local recurrence. With the rise of the TME procedure, with its low recurrence rate, it is now reinvestigated what adjuvant therapy is best in optimizing local recurrence rates and long-term survival. Survival benefits for most regimes have to be proven again and benefits of adjuvant therapy have to be weighed against additive morbidity. In a recent publication, Kapiteijn et al showed that significantly less local recurrences occur after short preoperative radiation with 5*5 Gy in patients with rectal cancer (overall recurrence rate 8.2 vs. 2.4 respectively)[1]. Although no survival benefit was found, this might be caused by the relatively short follow-up of 2 years. The operative procedure was extensively standardized and

Post-operative chemotherapy is not standard treatment in rectal cancer. Chemotherapy is predominantly applied in randomized clinical trials.

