5 STUDY DESIGN

This trial is a randomized, international, multi-center study comparing laparoscopic and conventional resection for rectal cancer. Patients will be accrued by the participating hospitals of the COLOR II study group. The COLOR II study group is an international group of surgeons with interest and expertise in laparoscopic and colorectal surgery. Since 1997 the COLOR I study group has performed and almost completed a large international randomized controlled trial comparing laparoscopic to open surgery for colon cancer. Many centers of the COLOR I study group will join the COLOR II study group.

The design involves allocation of all suitable consecutive patients with rectal carcinoma to either of the two procedures at a randomization ratio of 2:1, in favor of the laparoscopic procedure. Excluded are patients with a carcinoma treated by local resection and palliative resections. The trial will be stratified according to participating center, resection type, preoperative radiotherapy and sex.

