10 RANDOMIZATION

Once eligibility has been established and patient details have been logged, the patient will be allocated to either laparoscopic or conventional operation. Randomization will be performed by computer at time of randomization. Randomization will be balanced and stratified by participating center, resection type, radiotherapy and sex. When patients are not subjected to the treatment modality as randomized, data will be analyzed on an "intention to treat basis" (once randomized, patients will not be excluded or changed groups because of conversion or type of resection).

Randomization for all centers will be done through internet:

www.color2.org (click "investigators")

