17.1 DATA COLLECTED AT RANDOMIZATION

At randomization, the clinician will be asked to give the following information through the internet:

- eligibility criteria fulfilled?
- randomizing physician / surgeon
- hospital (+fax number)
- kind of operation planned
- sex of patient
- date of birth
- clinical TNM stage

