17.2 DATA COLLECTED DURING PRE-OPERATIVE PERIOD

- ASA class
- length and weight
- number of previous abdominal operations
- date of diagnosis
- location of tumor
- proposed type of resection
- previous radiotherapy of the pelvis
- preoperative radiotherapy

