19 STATISTICAL CONSIDERATIONS

19.1 SAMPLE SIZE AND STATISTICAL ANALYSIS

Locoregional cancer recurrence rate of operated patients with cancer stages <IV after 3 years is currently about 10 %. The primary objective of the study is to show that laparoscopic surgery does not lead to an increased locoregional recurrence rate. Equivalence of both treatments is considered to be shown if the resulting two-sided 95% confidence limits of the difference in 3-yrs locoregional recurrence rates excludes a difference greater than 5%. At a randomization ratio of 2:1, and assuming a recurrence rate of 10% in each group, 850 laparoscopic patients and 425 open patients are required to have a power of 80% for this study.

All analyses will be carried out on an "intention to treat" basis: patients, whose randomized laparoscopic operation was converted to an open resection, will be analyzed in the laparoscopic group.

Eight weeks operative mortality, pathological resection margins and complication rates will be compared using the Chi-square test. Locoregional recurrence rate, disease free survival and overall survival will be compared between the two procedures using log-rank statistic, adjusted for center. Exploratory analysis of the prognostic effects of various baseline data will be done using multivariate Cox-regression. Analysis of the primary endpoint will be performed 1.5 - 2 years after inclusion of all patients.

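### Randomization is stratified on four factors, but section 19.1 adjusts the log-rank tests for center only, and the section 17.1 randomization entry list omits one stratum, radiotherapy

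*Protocol*

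**What the plan says.** Three sections of the protocol name the same four stratification factors, with small differences in wording.

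- Section 10: "Randomization will be balanced and stratified by participating center, resection type, radiotherapy and sex".
- Section 3.4: "Randomization is stratified for each participating center, planned procedure, radiotherapy and sex".
- Section 5: "The trial will be stratified according to participating center, resection type, preoperative radiotherapy and sex".

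Section 10 also says that a computer makes the allocation at the moment of randomization, over the internet.

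Section 17.1 opens with "At randomization, the clinician will be asked to give the following information through the internet" and gives seven items: eligibility, randomizing physician, hospital, planned operation, sex, date of birth and clinical TNM stage. Radiotherapy is not one of them. The entry "preoperative radiotherapy" is in section 17.2, the pre-operative data, and again as item 16 of the preoperative case record form.

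Section 19.1 compares the time-to-event outcomes "using log-rank statistic, adjusted for center". For the binary safety and pathology outcomes it says: "Eight weeks operative mortality, pathological resection margins and complication rates will be compared using the Chi-square test". Equivalence is judged by a two-sided 95% confidence interval for the difference in 3-year locoregional recurrence, for which no adjustment is stated. Cox regression appears only as an exploratory look at prognostic factors.

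**The concern.** There are two mismatches.

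**Analysis against design.** Stratified randomization balances the arms on the factors used, which reduces the true variance of the treatment difference. An analysis that leaves those factors out keeps their contribution in its standard error. The interval is then wider than it need be, and some power is lost. Section 19.1 does not leave the adjustment open for the log-rank tests. It names center and stops, so an analysis plan that adjusted for all four factors would depart from the protocol text.

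**Data capture against design.** A computer can stratify only on what it is given. Three of the four factors are on the 17.1 list and radiotherapy is not. If the list is complete, balance on radiotherapy is left to chance.

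Radiotherapy is a factor the protocol itself links to the primary endpoint. Section 4.5 cites a randomized trial of short preoperative radiation with "overall recurrence rate 8.2 vs. 2.4 respectively", a ratio of 8.2/2.4 = 3.4. The trial has little power to spare, because it is sized almost exactly at 80%.

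**Working it through.** **Inputs.** From section 19.1: 10% recurrence in each arm, margin 5 percentage points, two-sided 95% interval, 850 laparoscopic and 425 open patients, power 80%. From section 4.5: recurrence 8.2% without and 2.4% with radiotherapy. Assumption: the irradiated share s, which the protocol does not give, is 50%, with a range of 30% to 70%.

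**1. The plan's own sample size.** With 2:1 allocation and z-values 1.96 and 0.8416:

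n(open) = (1.96 + 0.8416)² × (0.09 + 0.09/2) / 0.05² = 423.8, rounded up to 424.

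This gives 424 + 848 = 1272, against the stated 425 + 850 = 1275, so the figure reproduces. At 850 and 425:

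- SE = √[0.09 × (1/850 + 1/425)] = 0.01782
- power = Φ(0.05/0.01782 − 1.96) = 80.1%

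This is power against an increase beyond the margin.

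**2. Variance explained by radiotherapy.** Scale the two rates so that the overall rate stays at 10%. At s = 50% they become 15.5% without and 4.5% with radiotherapy.

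- Between-group variance: s(1 − s)(0.155 − 0.045)² = 0.0030
- Share of the total 0.09: 3.3%
- SE with that part removed: √[0.087 × (1/850 + 1/425)] = 0.01752, which is 1.7% smaller

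**3. Stratified and then ignored.** The true SE is 0.01752 but the analysis uses 0.01782.

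- Power unadjusted: Φ[(0.05 − 1.96 × 0.01782)/0.01752] = 80.5%
- Power adjusted: Φ(0.05/0.01752 − 1.96) = 81.4%
- Actual two-sided alpha unadjusted: 2 × [1 − Φ(1.96 × 0.01782/0.01752)] = 0.046

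| Irradiated (assumed) | Variance share | Two-sided alpha, unadjusted | Power, unadjusted | Power, adjusted |
|---|---|---|---|---|
| 30% | 1.9% | 0.048 | 80.3% | 80.8% |
| 50% | 3.3% | 0.046 | 80.5% | 81.4% |
| 70% | 4.6% | 0.045 | 80.7% | 81.9% |

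**4. Not stratified on radiotherapy, because it was never entered.** The unadjusted SE of 0.01782 is then valid, alpha is nominal and power is 80.1%. Adjusting in the analysis still brings power to about 81.4%, a gain of 1.3 points.

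**5. How the adjustment is made.** The preoperative form lists three proposed resection types. Three types × 2 radiotherapy × 2 sex = 12 cells per center. The number of centers is not given. If 30 is assumed, there are 360 cells with 1275/360 = 3.5 patients each. About 0.10 × 1275 = 128 events would be spread over them, or 0.35 per cell. Full cross-stratification could therefore lose more than it gains. If sparse cells retained only about 90% of the information, power would be Φ(0.05/0.01752 × √0.90 − 1.96), about 77%, below the unadjusted 80.5%.

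**The case against.** **The center-only phrase does not govern the primary decision.** It qualifies the log-rank tests, whereas equivalence rests on the interval for the 3-year difference. This stands. How that interval is adjusted could also be settled in an analysis plan that is not shown, so silence there is not in itself an error. The explicit center-only wording for the log-rank tests remains out of line with the design.

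**The two mismatches do not both cost power in the same way.** Either radiotherapy was stratified and the unadjusted interval is too wide, or it was not and the interval is valid. This also stands. It is why the gain is about 0.9 points in the first case and 1.3 only in the second.

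**The radiotherapy contrast is borrowed.** It comes from another study with about two years of follow-up. Here section 14.1 leaves preoperative treatment to local standards and the surgeon's preference. If higher-risk patients are irradiated, the contrast may be weaker, and center adjustment may already absorb part of it. The figures in the table are therefore illustrative.

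**Center only is a reasonable choice when strata are sparse.** This holds against full cross-stratification, as step 5 shows. It does not hold against a main-effects model.

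**Stronger readings that the documents do not support.** A reader might infer that radiotherapy is recorded only after the allocation is known and so may depend on the arm. The preoperative form does carry an arm label in its header. But section 17.2 gives no timing relative to allocation, and it repeats the proposed resection, which is already asked at randomization. Section 10 has patient details logged before allocation, and section 14.1 requires equal preoperative protocols in both arms. A reader might also call radiotherapy the strongest prognostic factor; no section ranks the factors.

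**Conclusion.** Both mismatches are in the text. Four factors define the randomization, one is carried into the log-rank comparisons, none is stated for the deciding interval, and one of the four is missing from the list of data entered when the computer allocates.

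The consequence is modest. If the strata are used and then ignored, the analysis is slightly conservative: about 0.9 points of power (80.5% against 81.4%) with half the patients irradiated, and a two-sided alpha of about 0.045 to 0.048 over 30% to 70%. These figures assume an overall rate of 10%, the 8.2 to 2.4 ratio, and no overlap between the radiotherapy and center effects.

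It would be wrong to conclude that the trial's inference is invalid or biased. Type I error is not inflated, the sample size reproduces and does not change, and radiotherapy status is still recorded on the preoperative form and can be analysed. Nor do the documents show that the web system fails to ask for radiotherapy; they show only that the stated list does not. This is a consistency correction with a small gain in precision, worth making because it is nearly free.

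**What to change.** - **Section 17.1:** add planned preoperative radiotherapy (yes/no) to the items entered at randomization, and use that same term in sections 3.4 and 10, which now say only radiotherapy. The preoperative form has a separate item for previous pelvic radiotherapy, so the distinction should be explicit.
- **Section 19.1:** replace the center-only adjustment with adjustment for resection type, preoperative radiotherapy, sex and center as recorded at randomization. Apply it to the 3-year risk difference that decides equivalence and to the supportive log-rank and Cox comparisons.
- **Method:** specify main-effects covariate adjustment, with small centers pooled or center as a random effect or shared frailty, and not full cross-stratification. Keep the primary result on the absolute risk-difference scale so that the 5-point margin still applies.

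The cost is one field on the randomization screen, a sentence in 19.1 and a slightly more complex model. The sample size does not change.

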21.7 APPENDIX VI: FLOW CHART OF RECTAL CANCER PATIENTS

21.8 APPENDIX VII: CASE RECORD FORMS

See next pages

COLOR II

Dept. of Surgery, QEII Health Sciences Centre
[name]
[name], Halifax, Nova Scotia
Canada [name]
[contact]
[contact]

Date:**Procedure:** LAP / OPEN**Rand nr:****Doctor:**

IDENTIFICATION (no 1 - 6)**If appropriate, please encircle correct figure, more than one can be encircled per question**

1. hospital :
2. randomization no. :
3. date of birth (dd/mm/yyyy) :
4. gender : 1 male
2 female
5. date of randomization (dd/mm/yyyy) :
6. randomized procedure : 1 laparoscopic
2 open
- 6A. clinical TNM stage: T _____ N _____ M _____

COLOR II

Dept. of Surgery, QEII Health Sciences Centre
[name]
[name], Halifax, Nova Scotia
Canada [name]
[contact]
[contact]

Date:

Procedure: LAP / OPEN

Rand nr:

Doctor:

PREOPERATIVE PERIOD < 28 days prior to surgery (no 7 - 17)

If appropriate, please encircle correct figure, more than one can be encircled per question

7. date of admission (dd/mm/yyyy):

8. ASA class :

9. length : cm

10. weight : kg

11. no. of previous abd. operations :

12. date of diagnosis (dd/mm/yyyy) :

13. exact location of tumor : cm (distal border from anal verge)

- determined by : 1 rectoscopy
- 2 colonoscopy
- 3 MRI
- 4 CT

14. proposed type of resection :

- 1 Resection without TME (= Partial Mesorectal Excision)
- 2 Resection with TME with preservation of the anus
- 3 Resection with TME without preservation of the anus (APR)

15. previous radiotherapy of the pelvis : 0 no
1 yes

16. preoperative radiotherapy : 0 no
(if yes, please specify dose and duration) 1 yes X Gy

16a. preoperative chemotherapy : 0 no
(if yes, please specify dose and duration) 1 yes

16b. Participation in Quality of Life substudy : 0 no
1 yes

COLOR II

Dept. of Surgery, QEII Health Sciences Centre
 [name]
 [name], Halifax, Nova Scotia
 Canada [name]
 [contact]
 [contact]

Date:**Procedure:** LAP / OPEN**Rand nr:****Doctor:****INTRAOPERATIVE PERIOD** (no 18 - 39)

If appropriate, please encircle correct figure, more than one can be encircled per question

18. name(s) of surgeon(s) :
- 18a. experience (last year) : < 10 lap colorectal procedures
 10 - 20 lap colorectal procedures
 > 20 lap colorectal procedures
19. date of surgery (dd/mm/yyyy) :
20. performed operative procedure : 1 resection without TME (= Partial ME)

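### The recurrence comparison is adjusted for center only, so it leaves unused some modest precision available from clinical T and N category and tumor height, all recorded before surgery

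*Protocol*

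**What the plan says.** Section 19.1 sets the decision rule on the absolute scale: "Equivalence of both treatments is considered to be shown if the resulting two-sided 95% confidence limits of the difference in 3-yrs locoregional recurrence rates" meets the condition "excludes a difference greater than 5" percentage points. The size follows from "assuming a recurrence rate of 10% in each group", with the statement that "850 laparoscopic patients and 425 open patients are required to have a power of 80% for this study". No covariates are named for that confidence interval.

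The same section says that locoregional recurrence, disease-free survival and overall survival are compared "using log-rank statistic, adjusted for center". The next sentence gives baseline data their only stated use: "Exploratory analysis of the prognostic effects of various baseline data will be done using multivariate Cox-regression". It does not list the variables.

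The information itself is on file before the operation. Section 17.1 lists "clinical TNM stage" among the items entered at web randomization, and the case record form repeats it as "6A. clinical TNM stage". Section 17.2 lists tumor location as a pre-operative item. Case record form item 13 records it in cm from the anal verge.

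Randomization is stratified by center, resection type, radiotherapy and sex (sections 3.4, 5 and 10). Clinical stage and tumor height are not on that list.

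**The concern.** The trial succeeds or fails on one confidence limit for a risk difference, and the design sits almost exactly at 80% power with no stated allowance for loss. Section 4.2 itself says that outcome after resection depends on stage. Adjusting a risk difference for pre-operative predictors of recurrence narrows its interval without adding patients, provided the result is still expressed as an absolute difference.

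Section 19.1 does more than stay silent on adjustment. It names center as the adjustment for the recurrence comparison and describes the use of baseline data as exploratory. A later analysis plan that put stage and height into the primary estimate would have to depart from that text. At stake is a small amount of power, and a covariate choice that is better fixed in advance than argued over once results are known.

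**Working it through.** **1. Reproduce the stated design.** Inputs from section 19.1: 10% in each arm, margin 0.05, two-sided 95% limits (1.96), 80% power (0.8416), ratio 2:1. The upper limit is the one that matters, since the stated aim is to exclude an increase.

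- Open arm: (1.96 + 0.8416)² × (0.09 + 0.09/2) / 0.05² = 7.849 × 0.135 / 0.0025 = 423.8, so 424. Laparoscopic 848, total 1272. The protocol has 1275.
- SE at 850 and 425: √(0.09/850 + 0.09/425) = 0.01782, or 1.78 points. Half-width 1.96 × 1.78 = 3.49 points.
- Power: Φ(0.05/0.01782 − 1.96) = 80.1%.

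The protocol's figure holds, and it does not depend on covariate adjustment.

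**2. Effect of adjustment.** For a standardized risk difference, approximately, adjusted SE = SE × √(1 − R²), with R² = Var[p(x)] / (0.10 × 0.90), where p(x) is the recurrence risk given the covariates.

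The protocol gives no prevalences or odds ratios. The following are assumptions: node-positive 40%, T3 60%, low tumor 35%, independent of each other, a common odds ratio (OR) for each, and the intercept set so that overall risk is 10%.

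| Common OR | R² | SE (points) | Half-width (points) | Power | Equivalent extra patients, 1275/(1 − R²) − 1275 |
|---|---|---|---|---|---|
| none | 0 | 1.78 | 3.49 | 80.1% | 0 |
| 1.5 | 1.07% | 1.77 | 3.47 | 80.5% | 14 |
| 2 | 3.15% | 1.75 | 3.44 | 81.4% | 41 |
| 3 | 7.81% | 1.71 | 3.35 | 83.2% | 108 |

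An OR of 4 for all three factors would give R² 12.1% and power 84.9%. That is strong for a population already narrowed by the eligibility criteria.

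A second assumed set (T3 60%, node-positive 40%, low tumor 30%) gives R² 2.4% and power 81.0% with ORs of 2, 2 and 1.5. With ORs of 3, 3 and 2 it gives R² 6.0% and power 82.5%.

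**3. Simulation check.** In 3000 simulated trials per setting (first assumption set), a standardized logistic estimate was compared with the raw difference. Variance fell by about 2.5% at OR 2 and 6.3% at OR 3, somewhat below the R² values. Put into the power formula:

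- OR 2: SE = 1.782 × √0.975 = 1.760; Φ(5/1.760 − 1.96) = 81.1%.
- OR 3: SE = 1.782 × √0.937 = 1.725; Φ(5/1.725 − 1.96) = 82.6%.

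**4. Where chance imbalance sits.** The shift in the risk difference due to random imbalance in the three factors has SD = √R² × SE. At OR 2 this is √0.0315 × 1.782 = 0.32 point; at OR 3, √0.0781 × 1.782 = 0.50 point. The remainder has SD √(1 − R²) × SE, which is 1.754 at OR 2. Since 0.316² + 1.754² = 3.18 = 1.782², the imbalance component is already inside the unadjusted SE.

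**The case against.** The strongest objection is that naming covariates for an adjusted estimate is ordinary content for an analysis plan, which is not to hand, and that section 19.1 does not forbid adjustment of the confidence interval. The second half is true: no estimator is fixed for the interval. But the section does name center as the adjustment for the recurrence comparison and does label the use of baseline data exploratory. That is a stated choice that can be improved, so the point survives as a suggestion on efficiency.

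The second objection is size, and it stands. The gain is one to three power points at assumed ORs of 2 to 3, and less at 1.5. Section 9.2 excludes T4 tumors and T3 tumors close to the endopelvic fascia, which narrows the range of risk. Resection type is stratified, and its form levels (partial excision, TME with the anus preserved, abdominoperineal resection) plausibly follow tumor height. Radiotherapy plausibly follows stage in part. The gain beyond the strata is therefore likely to be smaller than in the table, and it cannot be computed from the protocol.

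Misclassified or missing N category would lower it further, and section 17.1 does not say whether the recorded stage precedes pre-operative treatment. The calculation also treats every 3-year outcome as known. Section 19.1 places the primary analysis 1.5 to 2 years after the last inclusion, so late entrants would be censored.

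A reader might infer three stronger things that the protocol does not support:

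- **The result is exposed to chance imbalance in stage as a separate harm.** It is not. Random imbalance does not bias a randomized comparison, and step 4 shows that the unadjusted interval already covers it. It is the same benefit seen from another side.
- **Nothing in the design balances these factors.** Stratification by resection type and radiotherapy probably does so in part.
- **T, N and height are assigned to the exploratory Cox model.** Section 19.1 names no variables, so this is only a likely reading.

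**Conclusion.** The point holds as a modest loss of precision. The sample size reproduces (1272 against 1275), power is 80.1%, and the unadjusted interval is valid. Using clinical T, clinical N and tumor height in the primary estimate would raise power to about 80.5% to 83% for assumed ORs of 1.5 to 3, most likely toward the lower end. The half-width would fall from 3.49 points to between 3.47 and 3.35. All of this rests on assumed prevalences and ORs, on independence of the three factors and on complete 3-year outcomes. It is a low-cost improvement worth making and corrects no figure in the protocol.

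**What to change.** In section 19.1, define the primary estimate as the 3-year difference in locoregional recurrence risk with its 95% limits, obtained by standardizing over the trial population a model that handles censoring. Include the four stratification factors, clinical T category, clinical N category and tumor height in cm from the anal verge. An adjusted hazard ratio would not serve, because the 5-point margin is an absolute difference.

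State also that:

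- the stage used is the value entered at randomization (form item 6A), not the clinical stage on the yearly follow-up form (item 61A) and never pTNM;
- unstaged N has its own category;
- small centers are pooled by a fixed rule, since only about 0.10 × 1275 = 127.5 recurrences are expected;
- the estimate without clinical T, clinical N and height is reported as a sensitivity analysis.

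The cost is a few sentences in the protocol, repeated in the analysis plan. It needs no new data items and no more patients.

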6 ENDPOINTS

6.1 PRIMARY ENDPOINT

- locoregional recurrence rate 3 years postoperatively

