15 FOLLOW-UP

15.1 FOLLOW-UP VISITS

For the COLOR II trial, clinical examination is performed every year for 7 years. More frequent follow-up visits and other investigations will not be obligatory but on indication or to the preference of the surgeon. At three years after surgery, a CT scan or MRI of the pelvis is performed to exclude local recurrences. Imaging of chest and liver is performed to assess distant metastases. For the sake of interim analysis, recurrences or deaths should be reported by fax to the coordinating center within 2 weeks of detection. Follow-up of patients with recurrent disease should continue at least 3 years after diagnosis of recurrence or until death.

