16.2 DEFINITIONS OF LOCOREGIONAL RECURRENCE

- rectal exam positive for rectal cancer
- positive MRI or CT
- positive cytology or histology of adenocarcinoma

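### The primary analysis is dated 1.5 to 2 years after the last inclusion, so late-enrolled patients will have incomplete 3-year status and no 3-year scan, and the sample size makes no allowance for this

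*Protocol*

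**What the plan says.** - **Endpoint.** Protocol section 6.1 defines it as "locoregional recurrence rate 3 years postoperatively". Sections 3.3 and 4.6 agree.
- **Decision rule.** Section 19.1 accepts equivalence if the "two-sided 95% confidence limits of the difference in 3-yrs locoregional recurrence rates excludes a difference greater than 5" percent.
- **Sample size.** Section 19.1 plans 850 laparoscopic and 425 open patients for 80% power, "assuming a recurrence rate of 10% in each group". No allowance for incomplete follow-up is stated.
- **Comparison.** Section 19.1 names a log-rank statistic adjusted for center.
- **Analysis date.** Section 19.1: "Analysis of the primary endpoint will be performed 1.5 - 2 years after inclusion of all patients".
- **Assessments.** Under section 15.1, "clinical examination is performed every year for 7 years". The pelvis is imaged once by schedule: "At three years after surgery, a CT scan or MRI of the pelvis is performed to exclude local recurrences". Beyond this, "More frequent follow-up visits and other investigations will not be obligatory but on indication or to the preference of the surgeon".
- **What counts as an event.** Section 16.2 lists a positive rectal examination, "positive MRI or CT", and positive cytology or histology.

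The length of accrual is not stated.

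**The concern.** The endpoint needs 3 years of observation from surgery, while the analysis date guarantees only 1.5 to 2 years from inclusion. Any wait between inclusion and surgery widens the gap. Whatever the accrual period, everyone included in its last 1 to 1.5 years is short of 3 years on the analysis date.

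The scan schedule adds to this. Before 3 years the only obligatory assessment is the yearly clinical examination: one visit for the last entrants if the analysis comes at 1.5 years, and at most two if it comes at 2 years. A recurrence that would first be shown by the scheduled scan cannot yet be seen in these patients.

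At stake is the power of the confirmatory comparison, because the sample size leaves no room for incomplete 3-year status.

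**Working it through.** **1. Reproduce the planned sample size.** Inputs from section 19.1: 10% in each arm, margin 5 percentage points, two-sided 95% limits (one-sided 0.025 at the upper limit), 2:1 allocation, 80% power.

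- Open arm: n = 0.10 × 0.90 × (1 + 1/2) × (1.960 + 0.842)² / 0.05² = 423.8, so 424. Laparoscopic arm: 848. Total 1272, against 1275 planned.
- At 850 + 425: SE = √[0.09 × (1/850 + 1/425)] = 0.01782. Then 0.05/0.01782 − 1.960 = 0.845, and power = 80.1%.

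The plan's figure is therefore a two-proportion non-inferiority calculation. It treats all 1275 patients as having known 3-year status and has 3 patients to spare.

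**2. Patients short of 3 years.** Let F be the years from last inclusion to analysis (1.5 or 2, section 19.1) and A the accrual period (assumed 3 to 6 years, uniform entry). Share short = (3 − F)/A.

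| A (years) | F = 1.5 | F = 2 |
|---|---|---|
| 3 | 50% (638) | 33% (425) |
| 4 | 37.5% (478) | 25% (319) |
| 5 | 30% (382) | 20% (255) |
| 6 | 25% (319) | 17% (212) |

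**3. Power with a Kaplan-Meier 3-year difference.** Late patients are kept and censored at the analysis date. The share of patients with potential follow-up of at least t years is G(t) = min[1, (A + F − t)/A]. The large-sample Greenwood variance per patient is v = S(3)² × ∫₀³ λ/[S(t)G(t)] dt, with S(3) = 0.90. Then SE = √[v(1/850 + 1/425)] and power = Φ(0.05/SE − 1.960). With G = 1 throughout, v = 0.09 and the 80.1% returns. Deaths and loss to follow-up are ignored.

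*Constant hazard.* λ = −ln(0.90)/3 = 0.0351. For A = 4 and F = 1.5: v = 0.1018, SE = 0.01896, 0.05/SE − 1.960 = 0.678, power 75.1%.

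*30% of recurrences first found at the 3-year scan (assumption).* 7% occur smoothly before 3 years, so λ = −ln(0.93)/3. The rest occur at t = 3 with conditional probability q = 1 − 0.90/0.93 = 0.0323. This adds q/[(1 − q) × 0.93 × G(3)] to the integral. For A = 4 and F = 1.5, G(3) = 0.625, v = 0.1153, SE = 0.02017, 0.05/SE − 1.960 = 0.518, power 69.8%.

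| A (years) | Constant hazard, F = 1.5 / 2 | 30% at scan, F = 1.5 / 2 |
|---|---|---|
| 3 | 72.6% / 77.2% | 64.2% / 72.2% |
| 4 | 75.1% / 78.1% | 69.8% / 74.7% |
| 5 | 76.3% / 78.5% | 72.5% / 76.0% |
| 6 | 77.1% / 78.8% | 74.0% / 76.8% |

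**4. Sensitivity to the scan share.** With 10% first found at the scan and A = 4, power is 73.2% / 76.9%. With 50%, it is 66.7% / 72.6%.

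**5. After the change.** With F = 3 counted from surgery, no patient falls short through late entry, G(t) = 1 up to 3 years, and power is 80.1% in every scenario.

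**The case against.** The strongest defence is that section 19.1 names a log-rank comparison. In a time-to-event analysis it is ordinary to cut the data before the last patient reaches the landmark; late entrants contribute censored time. How the 3-year difference and its interval are estimated may be set out in an analysis plan that is not shown. This stands in part: it is why the power figures above keep the late patients. It does not remove the conflict. The protocol itself fixes the date, its decision rule is an interval on 3-year rates, and its sample size assumes complete 3-year status.

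The size of the loss is also open to challenge, and rightly. It depends on an accrual period and a scan-detected share that the protocol does not give. Constant hazard is not a best case: if recurrences cluster early, the loss shrinks. In the limit where the analysis is at 2 years and every recurrence surfaces within 2 years, a Kaplan-Meier estimate loses nothing.

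Three stronger readings are tempting, and the protocol does not support them:

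- *Late-enrolled patients cannot have the endpoint at all.* They can. Section 16.2 sets no minimum time, and a recurrence found at a yearly visit or on an indicated test counts.
- *Power falls to that of complete 3-year patients only* (51-73% over the same accrual range). That would mean discarding everyone with shorter follow-up, which the protocol nowhere plans.
- *The result would be skewed toward an early learning curve.* This is speculation. Sections 8 and 20.3 require experience before trial operations, and a center that joins late starts its own experience late.

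Nor is bias between the arms shown. One calendar cut-off applies to both arms and randomization is stratified by center, so late-entry censoring should be balanced.

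**Conclusion.** The point holds: the analysis date in section 19.1 does not fit the 3-year endpoint, the 3-year decision rule or the single scheduled pelvic scan. This does not depend on any assumption.

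Its size does. Under uniform accrual over 3 to 6 years, 17-50% of patients (212 to 638) are short of 3 years at the analysis. Kaplan-Meier power is about 73-79% with a constant hazard, a loss of roughly 1 to 7 points from 80.1%. It is 64-77% if 30% of recurrences are first found at the scan. The loss is smaller if recurrences occur early.

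The harm is lost precision, together with scan-detected recurrences that are unseen in late enrolees. It should not be read as a biased comparison or as an absence of endpoint data in these patients.

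**What to change.** Replace the timing sentence in section 19.1 with: *The primary endpoint is analysed when the last operated patient has reached 3 years after surgery plus the scan window.* State the length of that window. Add that a locoregional recurrence found at the scheduled 3-year scan counts as a 3-year event, so that a scan performed slightly late is not lost from the 3-year rate.

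The cost is one amended sentence and a primary report that comes 1 to 1.5 years later. The number of patients and the visits do not change, since follow-up already runs to 7 years.

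If the earlier date is kept, specify a Kaplan-Meier difference in 3-year rates with its confidence interval as the primary analysis, justify the minimum follow-up, and restate the power for that date with the accrual period and the assumed timing of recurrences made explicit.
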